8.4 Data Presentation Conventions

Continuous safety variables (e.g., clinical laboratory values and vital signs) will be listed to the same precision as the source data. Derived variables will be calculated and listed using the same precision as the value(s) from which they were derived.

For the tabular reporting of descriptive statistics:

- Continuous variables: the same number of decimal places as in the raw data will be presented when reporting minimum and maximum, 1 more decimal place than in the raw data will be presented when reporting mean and median, and 2 more decimal places than in the raw data will be presented when reporting SD.
- Categorical/discrete variables: the frequency count and the percentage (of available data) for each class of the variable will be presented and will be displayed in the form XX (XX.X%) where the percentage is in the parentheses. All percentages will be presented to 1 decimal place, unless otherwise specified. Percentages equal to 100

will be reported as 100% and percentages will not be presented for zero frequencies.

Unless otherwise specified, percentages will be calculated based on the number of subjects specified by the appropriate population definition.

- Date variables: formatted as DDMMYY for presentation. Time will be formatted in military time as HH:MM for presentation.

Extra measurements (such as unscheduled or repeat assessments) will not be included in summary tables but will be included in subject listings. They will be used in summary tables which are not “time specific”, for example, summaries of maximum post dose values.

All tables, listings, figures will be produced in landscape orientation using Times New Roman 9-point font. Output files will be created in rich text file (RTF) format.

Missing or invalid data will be generally treated as missing, not imputed, unless otherwise stated (see Section 9.5).

The table, figures and listing shells and table of contents as part of this SAP provide the expected layout and titles of the tables, listings and figures. Any changes to format, layout, titles, numbering, or any other minor deviation will not necessitate a revision to the SAP nor will it be considered a deviation from planned analyses. Only true differences in the analysis methods or data handling will necessitate such documentation. The appropriate listings supporting the tables will be included and are not specified in the individual sections throughout the document.

Minor modifications may be necessary to the planned design of tables, listings and figures to accommodate data collected during the actual study conduct. Any major deviations from the final approved SAP (e.g., change in the population used, change from statistical method/assumption listed, transformation of data type [e.g., continuous data transformed to categorical], exclusion of planned analysis, etc.) or additional unplanned analyses will be documented (with justification) in the CSR.

8.5 Treatment Comparisons

The following labels for treatment groups will be used on all tabulations, in the following order:

| CAP-1002 (N=00) | Placebo (N=00) | Total (N=00) |
|--------------------|-------------------|-----------------|
|--------------------|-------------------|-----------------|

8.6 Definitions, Computations, Derived Data

- Screening: Screening is defined as 3-4 days prior to Day -1 prior to the first study drug administration.
- Baseline: Measurements taken at Screening or prior to receiving the first dose of study drug; whichever is latest.
- Visit Nomenclature: Nominal visits nomenclature on the CRFs and the scheduled visit will be used for summary tables (i.e., visit, timepoint, etc.).
- 1 year = 365.25 days. Year is calculated as (days / 365.25) and will be rounded to 1 digit after the decimal point (tenths) for presentation purposes.
- 1 month = 30.4375 days. Month is calculated as (days / 30.4375) and will be rounded to 1 digit after the decimal point (tenths) for presentation purposes.
- 1 pound = 0.454 kg and 1 kg = 2.2 pounds.
- 1 inch = 2.54 cm and 1 cm = 0.3937 inches.
- Body mass index (BMI) calculated as [weight (lbs) / height (in)²] x 703.

9. GENERAL CONSIDERATIONS FOR DATA ANALYSES

Due to the dynamic nature of COVID-19 clinical practice and changing knowledge of relevant outcome measures, the SAP reflects recent changes in the understanding of the clinical meaningfulness of the efficacy outcomes. All analyses are prespecified because the blind has remained intact for this study.

The currently supported version of SAS software (9.4 or later) will be used to perform all data analyses. The actual SAS version used will be presented in the Clinical Study Report.

All data in the database will be presented in the data listings. Unless otherwise stated, all listings will be sorted by treatment group, subject number and assessment date/time.

Unless otherwise stated, continuous variables will be summarized using descriptive statistics including number of non-missing observations, mean, standard deviation, median, minimum and maximum values. Categorical variables will be summarized with frequency counts and percentages. The population size (N for sample size and n for available data) and the percentage (of available data) for each class of the variable will be presented.

In general, only data from nominal protocol scheduled visits will be included in the summary tables. They will be used in summary tables which are not “time specific”, for example,

summaries of maximum post dose values. Data from unscheduled visits will not be included in the summary tables but will be included in the listings.

The mITT analysis population will be the primary basis for all analyses in this study.

9.1 Multicenter Studies

Data will be pooled across all investigative sites that enroll subjects.

9.2 Other Strata and Covariates

Not applicable for this Phase 2 study.

9.3 Examination of Subgroups

Treatment effects will be compared across the continuum of severity of COVID as defined by a combination risk score with the expectation that more severe cases may offer more chance for detecting treatment differences. Multiple Comparisons and Multiplicity

Efficacy endpoints will be tested sequentially in hierarchical order with primary outcomes followed by secondary outcomes. The totality of evidence across the primary and secondary endpoints will be considered in evaluating the proof of concept for this treatment.

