11. EFFICACY ANALYSIS

The modified Intent-to-Treat Population (as Treated) is defined as all enrolled and randomized subjects who received any amount of study treatment; the mITT population will be utilized for all efficacy analyses. All summary tables will be displayed by treatment arm.

This is a Phase 2 proof of concept study, so a hierarchical testing order will be specified, but p-values will be utilized for descriptive purposes even if a step in the hierarchy is not met and there will be no adjustment for multiplicity of analyses. In addition to the analysis by severity of COVID risk at baseline, additional subgroup analyses will be conducted on an ad-hoc basis and will be fully described in the clinical study report.

The primary analysis for each efficacy endpoint will be as follows, unless otherwise noted in the corresponding section. A Cox Proportional Hazards (PH) model will be utilized to characterize overall survival or time-to-event, correcting for baseline COVID severity risk score. This risk score will be calculated based on historical data and will include baseline characteristics of age, weight, sex, and presence of comorbidities. In addition, unadjusted Kaplan-Meier curves will be presented by treatment group and summary statistics will include estimates of median survival (and corresponding 95% confidence interval), minimum and maximum time, and the number of censored subjects. The overall survival time will be compared between the treatment arms using a log-rank test.

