11.2 Ordinal Scale of Clinical Improvement

Since there are 9 categories of the WHO Ordinal Scale of Clinical Improvement and these categories are ordinal in nature (higher score correlates to a higher severity level) it is possible to analyze this endpoint as a continuous scale variable.

The mean change in the WHO Ordinal Scale of Clinical Improvement at each timepoint will be compared between treatment groups using a mixed model with repeated measures (MMRM), with baseline score and weighted COVID severity risk score as covariates. Due to the small sample size and unknown variances for the two independent treatment groups, a test for equal variances and normality will be applied prior to choosing the inferential

statistical method to employ. If the test for equal variances and normality is > 0.10 (indicating that the variances are not significantly different and the data is close to normally distributed) the parametric MMRM will be used to test for treatment group differences. If the test for equal variances or normality is ≤ 0.10 (indicating that the variances are significantly different, or the data is non-normally distributed) then a non-parametric MMRM will be used.

The model will test the null hypothesis that the differences in least-square (LS) means between the active and placebo groups over 90 days is equal to zero. LS means will be estimated at each visit along with treatment differences, p-values, 95% confidence intervals for the difference in LS means, and an effect size based upon Cohen's D will be provided for treatment comparisons.

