16. ORDINAL SCALE FOR CLINICAL IMPROVEMENT

A special World Health Organization (WHO) committee developed the Ordinal Scale for Clinical Improvement to help measure the severity of COVID-19 over time.

| Patient State | Descriptor | Score |
|--------------------------------|--|--------------|
| Uninfected | No clinical or virological evidence of infection | 0 |
| Ambulatory | No limitation of activities | 1 |
| | Limitation of activities | 2 |
| Hospitalized Mild Disease | Hospitalized, no oxygen therapy | 3 |
| | Oxygen by mask or nasal prongs | 4 |
| Hospitalized Severe Disease | Non-invasive ventilation or high-flow oxygen | 5 |
| | Intubation and mechanical ventilation | 6 |
| | Ventilation + additional organ support – pressors, RRT, ECMO | 7 |
| Dead | Death | 8 |
| [REDACTED] | | |

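### The SAP's analysis of treatment effect by COVID severity uses a score that names only prognostic risk factors, so it does not directly test its stated expectation about sicker subjects

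*SAP*

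**What the plan says.** SAP 9.3 (Examination of Subgroups) states: "Treatment effects will be compared across the continuum of severity of COVID as defined by a combination risk score", and gives the reason: "with the expectation that more severe cases may offer more chance for detecting treatment differences". It does not define the score.

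SAP 11 (Efficacy Analysis) describes one score, used to adjust the Cox models: "This risk score will be calculated based on historical data and will include baseline characteristics of age, weight, sex, and presence of comorbidities". Just before this, the same section refers to the planned subgroup work: "In addition to the analysis by severity of COVID risk at baseline, additional subgroup analyses will be conducted on an ad-hoc basis". No weights, historical source or interaction model are given.

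SAP 11.2 specifies the repeated-measures model for the ordinal scale "with baseline score and weighted COVID severity risk score as covariates". SAP 16 says that a WHO committee "developed the Ordinal Scale for Clinical Improvement to help measure the severity of COVID-19 over time".

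Protocol 9.4.7 marks subgroup analyses as not applicable, so it offers no other definition of severity. The schedule in Protocol 1.3 has the ordinal scale and respiratory status recorded on Day 1 before infusion.

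**The concern.** The question in SAP 9.3 is about severity of disease, but the components named for the score are host characteristics. Age, weight, sex and comorbidities say who is likely to do badly. They do not say how ill the subject is when infused. Oxygen support, ordinal category, oxygenation, ARDS grade and inflammatory markers are all absent from the list.

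This is the only effect-modification analysis the SAP specifies in advance; any others are ad hoc. If it is reported under a severity label, a positive result would be credited to clinical severity when it reflects prognostic risk. A null result could be taken as evidence that severity does not matter. Either could mislead the choice of population for the further studies that the trial is meant to support.

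**Working it through.** **Step 1: which score is meant.** SAP 9.3 leaves its combination risk score undefined. SAP 11 describes a baseline COVID severity risk score and, in the preceding paragraph, mentions the analysis by severity of COVID risk. No other score appears in either document. Treating the two as the same is an inference, but the text offers no alternative.

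**Step 2: how severity is used elsewhere in the SAP.**

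| Place | What stands for severity |
|---|---|
| SAP 3.2, area-under-curve endpoint | Ordinal scale |
| SAP 16 | Ordinal scale |
| SAP 11.10 | Berlin ARDS category, 0 to 3 |
| SAP 11.2, covariates | Baseline ordinal score and risk score, as two separate terms |
| SAP 9.3 with SAP 11 | Risk score: age, weight, sex, comorbidities |

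The two terms in SAP 11.2 show that the SAP itself treats baseline clinical status and the risk score as different quantities.

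**Step 3: whether another planned analysis answers the question.** In SAP 11.2 the baseline ordinal score is a main-effect covariate, which does not show whether the treatment effect varies with it. The Cox models are described as "correcting for baseline COVID severity risk score" and have no term for baseline clinical status. No section plans a treatment by baseline-status interaction.

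**Step 4: illustration of the attenuation.** There is no plan figure to reproduce: SAP 4 says information was inadequate for a formal sample size calculation. The documents supply N = 60 and 1:1 allocation. The assumptions are two-sided alpha 0.05, residual SD 1, a linear interaction, jointly normal scores, a true slope b (outcome SD per SD of severity) and a correlation r between the score and severity.

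- Standard error of the interaction: 2/√60 = 0.258.
- Slope seen on the score: r × b.
- Power: Φ(r·b/0.258 − 1.96) + Φ(−r·b/0.258 − 1.96).

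With b = 0.5:

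| r | Slope seen | Slope/SE | Power (formula) | Power (simulated, 1,500 trials each) |
|---|---|---|---|---|
| 1.0 (direct measure) | 0.50 | 1.94 | 49% | 45% |
| 0.5 | 0.25 | 0.97 | 16% | 14% |
| 0.3 | 0.15 | 0.58 | 9% | 7% |
| 0 | 0 | 0 | 5% | 5% |

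Over other assumed slopes, by formula: b = 0.3 gives 21%, 9% and 6% at r = 1, 0.5 and 0.3; b = 0.73 gives 81%, 29% and 14%.

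**Step 5: what the ordinal score can offer.** Protocol 5.2 excludes intubated subjects and those on ECMO or HFOV, and eligibility is reconfirmed on Day 1, so Day 1 scores should lie mainly at 3 to 5. If they were split evenly between 4 and 5 (an assumption), one SD would be √(0.5 × 0.5) = 0.5 points. A slope of 0.5 per SD would then mean 0.5/0.5 = 1.0 outcome SD per ordinal point, which is large. The 95% confidence interval would be about ±1.96 × 0.258 = ±0.51 per SD, or ±1.01 outcome SD per point.

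**The case against.** The strongest reply is that comparing treatment effect across baseline prognostic risk is a recognised approach. Higher-risk subjects have more events, which fits the stated hope of a better chance to detect differences, and section 11 already speaks of COVID risk. On that reading only the label needs changing. This stands as a reason to keep the risk analysis. It does not make that analysis a test of severity, which is what SAP 9.3 says it is.

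Other points stand and limit the claim. The study is an exploratory pilot with descriptive p-values, and no decision rule rests on this analysis. An ordinal-score interaction could be run ad hoc, although it would not be pre-specified. The Day 1 score has a narrow range, and at about 60 subjects an interaction is poorly estimated on either variable.

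A reader might also infer more than the documents support:

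- *That the score certainly contains no severity item.* Section 11 says what the score will include, which may not be a full list. Section 11.2 makes it unlikely that the ordinal score is inside it, but does not rule out other acute measures.
- *That the analysis cannot reveal anything about severity.* If the score correlates with acute severity, it carries a weakened signal, mixed with the effects of its own components.
- *That it is purely a demographic interaction.* Weight and comorbidities are named components.
- *That an older subject with comorbidities on no oxygen would rank above a younger one on high-flow oxygen.* Without weights, no such ranking can be stated.

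**Conclusion.** The concern holds in this form: the variable named does not match the question asked. As written, SAP 9.3 with section 11 tests effect modification by baseline prognostic risk and does not directly test whether clinically sicker subjects benefit more. This rests on reading the two scores as one and on the components that the SAP names.

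Under the linear model, any true severity interaction would be shrunk by the correlation between score and severity. That correlation is not in the documents, so the real loss cannot be calculated. The power figures above illustrate the mechanism under assumed slopes and correlations and are not estimates for this trial. The consequence is one of interpretation in an exploratory study, but the mismatch is clear and cheap to repair.

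**What to change.** Before unblinding, amend SAP 9.3 in two ways.

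1. Specify the severity analysis as a treatment by Day 1 pre-infusion ordinal score interaction. In the SAP 11.2 model the baseline score is already a covariate, so only the interaction is new; a Cox version would also need the score's main effect.
2. Keep the existing score as a separate analysis labelled baseline prognostic risk, and state its full components, weights and historical source.

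Report the interaction as an estimate with a confidence interval, and say that a null result is not to be read as no difference by severity.

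The data are already scheduled, so the cost is SAP wording and one more exploratory interaction. Its drawback is low power at about 60 subjects, with a baseline score likely confined mainly to 3 to 5.

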9.4 Missing Data and Dropouts

The issue of how to handle missing data caused by dropouts in clinical studies is a research topic that is still under development in the statistical literature. As has been noted in the ICH-E9 guideline, “no universally applicable method of handling missing values can be recommended”. The best approach is to minimize the chance of dropouts at the design stage of the clinical study and during study monitoring.

In general, data will be analyzed as received from the clinical database. Hence, missing values will not be replaced by imputed values except for the following situations:

9.4.1 Adverse Events

Adverse events with missing or partial dates will be handled such that in the absence of contradictory information an AE is classified as “treatment emergent”. So, for a missing start date (where the stop date is after the date of first study drug administration) the start date will be imputed as the first study drug administration date. Similarly, for a missing stop date, the stop date will be imputed as the date of last visit.

- If a partial date is recorded, the following convention will be used to assign the AE: If a start date is missing the day information and the month/year is the same as the first

study drug administration date, then use the first study drug administration date, else “01” will be used for the day. If a start date is missing the month and the year is the same as the first study drug administration date, then use the first study drug administration date, else “January” will be used for the start month.

- If a stop date is missing the day information and month/year is the same as the last study date, then use the last study date, else the last day of the given month will be used for the stop day. If a stop date is missing the month and the year is the same as the last study date, then use the last study date, else “December” will be used for the stop month.

9.4.2 Concomitant Medications

If the stop date of a concomitant medication is missing, then the medication will be treated as ongoing. If the start date of a medication is missing, the stop date will be used to determine whether or not it is concomitant. Medications with other incomplete start dates will be identified as concomitant using the same algorithm as above for TEAE if the stop date information is insufficient for the determination.

If start date is missing, the medication will be considered to have started prior to the study. It may also be considered concomitant, depending on the stop date or lack thereof.

9.4.3 Other Situations

For subjects who are withdrawn from the study prior to study completion, all data compiled up to the point of discontinuation will be used for analysis. All withdrawals will be included in all analyses up to the time of withdrawal.

Extra measurements (such as unscheduled or repeat assessments) will not be included in summary tables but will be included in subject listings. They will be used in summary tables which are not “time specific”, for example, summaries of maximum post dose values.

The original data will always be presented in the listings.

10. STUDY POPULATION

All disposition, baseline and demographic, efficacy, and safety analyses will be conducted on the Intention-to-Treat (mITT) as treated population and displayed by treatment group.

10.1 Subject Enrollment and Disposition

Enrollment will be summarized for all mITT subjects (defined as those subjects who signed informed consent form, were randomized, and received Investigational Product). The summary of enrollment will be presented by investigator site.

The subject disposition will be summarized on the mITT population and will include:

- The number of subjects who were enrolled and treated with study drug (mITT population).
- A summary of subjects who complete the study through Day 90.
- A summary of the primary reason subject did not complete through Day 90.

A listing of subject enrollment and disposition will be provided for all enrolled subjects. A listing of whether or not all inclusion and exclusion criteria were met and if not, which criteria were not met, by subject, will also be presented.

10.2 Protocol Deviations

The protocol deviations will be summarized by the deviation category as collected on the eCRF. All protocol deviations will be displayed in the subject listings.

10.3 Demographics

Demographic characteristics will include age, gender, child-bearing potential, race, and ethnicity.

The categorical (discrete) variables will be summarized using counts and percentages. The continuous variables will be summarized using mean, median, standard deviation, and range (maximum, minimum). All demographic data will be listed by subject.

10.4 Baseline Characteristics, Initial COVID-19 Diagnosis

Baseline characteristics of initial COVID-19 diagnosis will include the following: time (days) from initial diagnosis (by RT-PCR at the investigational site) to date of informed consent, time (days) from initial diagnosis to date of hospitalization, previous diagnosis confirmed test, previous ventilation support use, Ordinal Scale for Clinical Improvement at initial diagnosis, and categories of the Ordinal Scale for Clinical Improvement.

The categorical (discrete) variables will be summarized using counts and percentages. The continuous variables will be summarized using mean, median, standard deviation, and range (maximum, minimum). All initial COVID-19 diagnosis data will be listed by subject.

